Family-managed care is critical in promoting quality of life (QOL) and health in Alzheimer's disease and other dementias. The Partners at Meals (PaM) intervention emphasizes focusing on more than just "changing" a PWD, but also intervening with the People with whom they interact and Place where meals occur. With this intervention, CGs and volunteers or staff at RCCs partner and modify mealtime at a point when the PWD is still able to express preferences and engage in the meal process, and develop a PWD-centered plan of mealtime care. Of note, our pilot work indicated that CG's report of mealtime behavior may be inaccurate because CG and other family members may overlook key cues/triggers to dysfunctional behavior. Thus, to **improve this identification process, a secure and HIPAA-compliant telehealth component (Doxyme)** is used to record dysfunctional behaviors displayed by the PWD on a 'tablet'. The CG interacts with their "partner" volunteer, the RCC staff or MUSC Interventionst (AIM 4) either through a real-time connection or sharing of the recorded file so that together, they can problem-solve issues and modify the plan of care. This CG-volunteer/ staff member partnership also fosters consistency across settings (AIMS 1-3), as well as imparts skills and self-efficacy for care management for both parties, improves QOL for the CG and the PWD, improves mealtime outcomes for the PWD, and promotes better health outcomes.

Research design. A randomized cluster-design trial will be conducted in two large RCCs with six sites that serve primarily white and African American PWDs. RCCs will be randomized to the **intervention condition (Partners at Meals; 2 sites)** or [**'enhanced usual care' (EUC)**] (4 sites). The primary unit of analysis is the PWD and CG: 60 PWDs, 60 CGs will be enrolled; it is estimated that up to 60 volunteers/staff/managers may be enrolled. The CG and RCC volunteer or staff member is another dyad for analysis, as is the RCC volunteer/staff member and the PWD. Additionally, RCC Managers at both PaM and EUC sites will be interviewed regarding barriers to implementation, ways to enhance the project, and possible causes of discharge of PWD from the study related to nutritional problems.

Additionally, to explore the feasibility of program replication and widespread adoption, an online

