global survey of Respite Care Providers and their respective agencies will be conducted on the use of telehealth/videoconferencing technologies to deliver individualized educational support services to families in-the-home.

Partners at Meals (experimental condition) uses the C3P Model to direct change in three key areas (place, person, PWD) whether at the RCC or in the home. In the intervention sites, project staff will train the RCC volunteers or staff members, who will train CGs to more effectively manage meals based on assessment at the Center, and will subsequently use the telehealth solution in the home. Tailoring the plan to the home is critical to family-managed sustainability. The intervention will be delivered through each CG-volunteer /staff member dyad, and each PWD-CG dyad will be enrolled for 6 months. CGs and staff/volunteers in the EUC condition will have training focused on CG needs alone for support from family and others to manage care. A comprehensive process evaluation plan will be used to monitor implementation and foster dissemination.

Specific Aims:

Aim 1: To use a repeated-measures, randomized control design to assess the relative efficacy of Partners at Meals (PaM) vs. enhanced usual condition (EUC) in terms of the following PWD outcomes at baseline, and one-month intervals: nutritional status (weight, photography of pre- and post-food consumed); dysfunctional behaviors at meals (Edinburgh Feeding in Dementia scale XL with additional fields and questions added); quality of life (QOL-AD)

Main hypothesis: Participation in PaM will be associated with improved weight maintenance and decreased dysfunctional mealtime behaviors (the latter of which is the presumed mechanism of change).

Aim 2: To assess the relative efficacy of the Intervention vs. EUC in terms of the following. CG: quality of life (Euro-QOL), burden (Zarit Burden Scale), depression (CES-D), and self-efficacy for managing meals at home; b) RCC volunteer or staff: self-efficacy for training and management of mealtime issues; c) RCC director/manager: satisfaction with the program and willingness to maintain the program post-funding.

Aim 3: Conduct a process evaluation and content analysis to assure adherence, feasibility (e.g. using the telehealth tablet at home), reach, and maintenance to inform dissemination and adoption.

Exploratory Aim 4: To assess efficacy and outcomes of PaM when research staff implements the Intervention.

B. Significance and Innovation:

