The project staff **under the supervision of the PI (SQ) will be trained in the use of the tele-health component** in of the intervention; she will also be available for further training and consultation. Research Staff will then train the volunteers or RCC Staff and the volunteers or RCC Staff will train the CGs in an initial training and at the same times for booster sessions and observations as the mealtime plan (above). After instruction in the use of the tablet, the CG will make monthly photos and films of a breakfast, lunch and dinner using the tablet provided. These images will either be **sent via a password-protected HIPAA compliant system – Doxy.me** to be evaluated by the Volunteer or RCC Staff and the research staff. Alternatively, the tablet can be brought to the respite care site and images downloaded there. In partnership with the Volunteer or RCC Staff, and research staff, a plan will be made to either continue the activities in the current plan or to revise it. The **plan will be made initially after enrollment based on the tele-health images and the evaluation measures** (see next section), then **monthly** for the remainder of the 6-month intervention; the CG and Volunteer or RCC Staff will document their agreed upon plan with the goal of the CG becoming the ‘lead’ in the planning as time progresses to promote sustainability. During the intervention, the CG and Volunteer or RCC Staff or MUSC Project Staff (AIM 4) will **meet at least monthly** at the RCC in a private room or via DOXY.ME on the Tablet to review progress and resolve issues; the research project staff will attend the first two of these meetings to assure fidelity and facilitate the process (the RD may be consulted during these times or more frequently if needed). Thus, the mealtime intervention is occurring, being evaluated and modified monthly, based on the Place/ People/ Person of the Partners at Meals model. The RCC administrator/manager, staff and volunteers (and possibly the

RD) will have planned interactions with the Program Manager at one-month intervals to assess use of resources, skills and beliefs of RCC staff, satisfaction with the program and suggestions for improvement.

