Administrators/Managers at the respite sites **will be interviewed** by the Program Manager every 3 months that the study is in place for satisfaction, willingness to continue the program after completion, any CG or volunteer dissatisfaction, and are asked for data regarding discharge or hospitalization of study participants to determine if the cause could be related to nutrition-related changes. The Administrator/Manager and the project staff will ‘check-in’ every month, or more often if needed, to report any urgent problems or issues that need a timely resolution. However, the Administrators/Managers will not be consented as they are not research subjects but engaged in research (Offsite form attached) and we will be collecting feasibility and evaluation/satisfaction information from them. **Formal evaluation** of the Volunteer or RCC Staff, CG and PWD will occur at baseline, monthly and at the end of enrollment (6 months) or earlier if the CG or PWD withdraw or are withdrawn (see next section).

If requested, a step-by-step outline of the sessions used to train the Volunteer or RCC Staff, and then the CG by the Volunteer or-RCC Staff as well as ‘booster’ sessions can be provided to the IRB, as well as weekly and monthly review activities accomplished by research team members.

Measures, data sources and collection. As noted in the Aims, there are key outcome measures of interest as well as mediating and moderating variables to address secondary aims. This briefly summarizes the primary outcome measures, describes the dependent measures to address the primary study aims and summarizes all measures, collection mode and timing. **All data will be collected at baseline, monthly and when completed – at 6 months** to approximate the effect of the PaM or EUC on the groups separately and in unison. All participants at both the PaM and EUC sites will receive all measures. The primary measures against which the study is powered lie with the PWD and are **weight change and change in dysfunctional behavior**.

1. Person with Dementia measures:

Demographics collected only at baseline:

- Functional Assessment Staging Scale – level of independence in physical activities
- Mini-Mental Status Examination – rates level of dementia
- Characteristics – age, race/ethnicity, primary diagnosis/ health problems with focus on swallowing problems and possible dysphagia

Outcomes collected baseline, monthly and completion

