- Body weight and caloric intake – weight before meal in street clothing less outer garments; intake measured by images taken with tablet pre- and post-meals at pre-arranged times
- Edinburgh Feeding in Dementia Scale (EdFED XL with added questions) – 24-item scale for dysfunctional meal-related behaviors (images from the tablet may assist in validating behaviors in question)
- Quality of Life in Alzheimer’s Disease (QOL-AD) – 13 item instrument used in person with MMSE as low as 4

2. Caregiver measures:

Demographics collected only at baseline

- Age, race/ethnicity, employment, relation to PWD, living arrangement, hours/day caring for PWD

Outcomes collected baseline, monthly and completion

- Center for Epidemiological Studies – Depression Scale (CES-D) – widely used in CG studies
- Zarit 12-item Burden Scale – rated 0 – 4, used in prior CG studies
- European Quality of Life (Euro-QL) – measures health-related quality of life
- Self-efficacy for Change – based on CP3 Model (developed in pilot work)

3. Volunteer or RCC Staff measures (AIMS 1,2 and 3):

Demographics collected only at baseline

- Age, race/ethnicity, preparation for volunteer role including coursework or classes or personal experience as CG, frequency of attendance, years in role

Outcomes

- Self-efficacy for Change – based on CP3 Model instrument (developed in pilot work)
- Performance measures – self-report of fidelity to treatment, carry out or change mealtime plan, address questions, training issues, progress and participation (developed in pilot work)

4. RCC Administrator/Managers measures

Demographics collected only at baseline

- Age, education, training, years in role, roles and responsibilities, role as CG

Outcomes

- Overall satisfaction of staff and CGs
- Satisfaction with implementation issues, satisfaction with program, willingness to continue
- Discharge status of any PWDs in study – to institutional care, hospitalized related to nutrition-related problems

Online Global Survey of RCC providers

An online global survey of RCC providers will be conducted using a researcher developed survey instrument. The survey will explore RCC telehealth/video conferencing capabilities, their use pre and post the onset of the COVID-19 pandemic, and RCC provider attitudes and opinions towards communicating and delivering individualized and in-the home educational support services to caregivers and their families with these types of technologies.

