E. Protection of Human Subjects

1. Risk to subjects:

a. Sample

The proposed study will include 60 persons with dementia (PWD) and 60 caregivers (CGs) from 5 respite care centers (RCCs), approximately 33-57 ADC volunteers or staff and administrators/managers (will participate but are not considered subjects). The total number of persons counted for the Enrollment Tables is 180 persons. Both the PWD and his/her CG will be enrolled in this study and the PWD must attend one of the RCC sites for care at least once weekly. Additionally, volunteers will be enrolled who are long-time (defined as volunteering for at least 3 months or longer), and are present at least weekly. RCC Staff will have current affiliation with or have worked at the RCC with the last 12 months and are amenable to commit to the 6 month length of the study.

This is a cluster-randomized trial so each RCC whether in the EUC or PaM groups will be added every 2 months. For both types of conditions, the involvement of these participants includes: recruitment, consent and enrollment into the study; gathering of baseline data including an analysis of the percent of food eaten pre- and post-meals via a still photo, other assessments collected by an in-depth interview that will take about 1 hour. At this point in the **Intervention (PaM) group**, a train-the-trainer program will now be shared with RCC staff in the intervention site and within two weeks, under the direction of the Program Manager and with input from the

Registered Dietician, the RCC volunteer or RCC Staff will work with the CG to devise an initial plan of care for the PWD; this plan will be operationalized both at home and in the RCC (see Intervention – Partners at Meals). Additional training for new volunteer and booster sessions are planned. Monthly the RCC volunteer or RCC Staff and CG ‘partnership’ (dyad) will meet to determine if the plan is still working, and if adjustments need to be made with the help of the Program Manager or his/her designated staff member, and Registered Dietician, if needed. The intervention lasts 6 months and during that time, data are collected every month. Reasons for withdrawal are: death, institutionalization, and discharge from the RCC. Additionally, the administrator/manager of the RCC will be interviewed every 3 months that the project is ongoing (could be up to 2.5 years) to determine their satisfaction with the project, use of resources, and willingness to sustain the project.

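### EdFED, a primary outcome, may be checked against tablet images, but meal films are described only for the PaM arm, so its ascertainment may differ by arm

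*Combined protocol and SAP*

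**What the plan says.** Section D, under Measures, data sources and collection, names the primary measures as "weight change and change in dysfunctional behavior". The second is scored on the EdFED XL at baseline, monthly and at 6 months. In the list of measures for the person with dementia, the EdFED entry adds that "images from the tablet may assist in validating behaviors in question". No rule follows on when this is done, by whom, or whether a score may change as a result.

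The Intervention (Partners at Meals) part of Section D says that, once instructed in the tablet, "the CG will make monthly photos and films of a breakfast, lunch and dinner using the tablet provided". The recordings are then sent "to be evaluated by the Volunteer or RCC Staff and the research staff". In Section A, the paragraph on the experimental condition says of the intervention sites that those trained "will subsequently use the telehealth solution in the home". On the comparator, the same paragraph says "CGs and staff/volunteers in the EUC condition will have training focused on CG needs alone". The fuller EUC descriptions in Section C (Study Overview) and Section E.1.a do not mention tablet filming.

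Section A also gives the reason for recording: in pilot work, caregiver report of mealtime behaviour "may be inaccurate because CG and other family members may overlook key cues/triggers to dysfunctional behavior".

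For both conditions, Section E.1.a describes "gathering of baseline data including an analysis of the percent of food eaten pre- and post-meals via a still photo", and the measures list includes tablet pictures before and after meals to estimate intake.

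**The concern.** A comparison of two arms needs the outcome to be ascertained in the same way in each. Here the plan allows a second source of evidence on a primary outcome, and the form of that source best suited to showing behaviour, film of a meal in progress, is described for one arm only. The protocol's own case for recording is that it improves on unaided caregiver report. If it does, a film-aided EdFED and an unaided EdFED are not the same measurement.

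The bias could run either way. Films might bring more behaviours to light in PaM and hide a real benefit. They might instead resolve doubtful items as absent and create an apparent benefit. Because reduced dysfunctional behaviour is also the presumed mechanism of the weight effect, an error here would carry into the interpretation of the other primary measure.

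**Working it through.** The documents say that the study is powered on these two measures but give no alpha, power, effect size, SD or intracluster correlation. There is no stated calculation to reproduce, so the check is mainly a comparison of text.

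**1. What each arm is described as having**

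| Item | PaM | EUC |
|---|---|---|
| EdFED at baseline, monthly, 6 months | yes | yes |
| Pictures before and after meals, for intake | yes | yes |
| Monthly films of three meals at home | described | not described |
| Image check of doubtful EdFED behaviours | allowed, no rule | allowed, but no films described to do it with |
| EdFED rater and blinding | not stated | not stated |

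**2. Which images are meant.** In the tele-health paragraph the word covers both photos and films. In the measures list, the entry just before EdFED uses it for pictures taken before and after meals. On the first reading, the validation material differs by arm. On the second it is common to both arms, but weak evidence of what happened during the meal. The text does not settle which is meant.

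**3. Whether change from baseline removes the difference.** Let a(arm, time) be the average amount by which the method of ascertainment moves the EdFED score. The bias in the PaM minus EUC difference in change is

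[a(PaM, follow-up) − a(PaM, baseline)] − [a(EUC, follow-up) − a(EUC, baseline)].

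If EUC is unaided throughout, the second bracket is zero. If PaM is film-aided at both times by the same amount, the first bracket is also zero. If PaM is unaided at baseline and film-aided later, the full film effect remains. Section E.1.a has baseline data gathered first and the PaM train-the-trainer programme starting after that. Caregivers learn the tablet through that programme, so the third case is the likeliest reading of the sequence.

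**4. How much a shift would matter (illustration only).** Assumptions not in the documents: 30 per arm (the stated 60 persons with dementia split equally), two-sided 5%, no clustering, and a spurious shift b in SD units of the analysed score. As a variant, if the 60 already includes the 25% over-enrolment, 60/1.25 = 48, or 24 per arm.

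- SE = √(2/n) = √(2/30) = 0.258.
- False-positive rate with no true effect = Φ(b/SE − 1.96) + Φ(−b/SE − 1.96). For b = 0.2: Φ(−1.185) + Φ(−2.735) = 0.121.
- Effect detectable with 80% power = (1.960 + 0.842) × 0.258 = 0.72 SD. Power left if the shift runs against PaM = Φ((0.72 − b)/SE − 1.96). For b = 0.2 this is 0.527.

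| b (SD) | False positive, 30 per arm | False positive, 24 per arm | Power left from 80%, 30 per arm |
|---|---|---|---|
| 0.1 | 6.7% | 6.4% | 67.5% |
| 0.2 | 12.1% | 10.7% | 52.7% |
| 0.3 | 21.3% | 18.0% | 37.4% |
| 0.5 | 49.1% | 41.0% | 13.7% |

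The table shows sensitivity to a shift. It does not estimate one.

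**The case against.** The strongest reply is that the plan gives all measures to participants at both PaM and EUC sites, at the same intervals, and that the image clause sits inside that list. EUC must have some tablet access, since tablet pictures are an outcome measure, and the statement about EUC training describes training, not data collection. This shows that tablet pictures exist in both arms. It does not show that films do: the tablet images listed as a measure are intake pictures, and films appear only in the intervention description.

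Several stronger readings are tempting, and the documents do not support them:

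- A reader might infer that EdFED scores are corrected from film. The text is permissive, is limited to behaviours in question, and nowhere says that a score is altered.
- A reader might infer that EUC has no films. That rests on where films are described; no sentence says so.
- A reader might infer that caregivers miss behaviours, so that films would mostly add them in PaM. Section A speaks of overlooked cues and triggers, which is not the same thing. The EdFED rater is also unnamed, and Section E.1.b lists checklist-based direct observation among the data sources, so scoring may not rest on caregiver report.
- A reader might put a size on the bias. Assuming that 10% to 30% of behaviours are missed and that the SD is half the mean gives 0.1/0.5 to 0.3/0.5, or 0.2 to 0.6 SD. With the SD equal to the mean, the range is 0.1 to 0.3 SD. Every input is assumed, the calculation applies images to every PaM score, and it treats a shift in level as a shift in change.

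The timing is not certain either. The initial mealtime plan draws on tele-health images, so the first films may fall close to baseline. If they informed the baseline score too, some or all of the shift would cancel. These points limit the claim to a risk. They do not remove it, because nothing in the plan rules out film-aided follow-up scoring in one arm only.

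**Conclusion.** The point holds as a risk of differential ascertainment on a primary outcome. Following the plan as written can leave follow-up EdFED film-aided in PaM and unaided in EUC, and no rule prevents it. This rests on two readings of the text: that the images in the EdFED entry include the films, and that film training in PaM follows baseline.

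Neither the size nor the direction of the bias can be obtained from the documents. The illustration shows only that, with about 30 per arm, even a modest shift would matter: 0.2 SD takes the false-positive rate from 5% to about 12%, or power from 80% to about 53%. It ignores clustering, although allocation is by two grouped Sites. An established difference between arms, or a stated amount of bias, would go beyond the text.

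**What to change.** In the EdFED entry of the measures list (Section D), state that the score used in the primary analysis comes from the same source and the same type of rater in both arms, and is completed before that month's tablet images are viewed. Name the rater and say whether that person is blinded to arm. Enter any image-validated score in a separate REDCap field, for use only in tailoring the mealtime plan and in a sensitivity analysis.

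Alternatively, if EUC dyads already film meals on the same schedule, say so and apply image validation identically in both arms.

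The first option costs about one sentence and one database field, with no extra rater. Its downside is that the primary score gives up the image check. It also reduces the bias without removing it: PaM caregivers will have reviewed earlier months' films, and if they are the informants, that may still affect what they report.

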Collaborating with the 2 respite care organizations and up to 180 subjects, a cluster design will be used to determine the efficacy of the Partners at Meals (PaM) train-the-trainer program compared to enhanced usual care (EUC). Two groupings of sites will be created in attempt to balance size and racial distribution: the largest site, which is racially diverse (The ARK), will be paired with a site (in the Respite Care Charleston system), which is not diverse: Together they will be one Site for treatment condition and analysis. The other four sites in the Respite Care Charleston system that together have approximately the same diversity and size, will be joined to create a second Site. These two Sites will then be randomized to PaM and EUC. All subjects (PWD, CG and RCC volunteers) will be followed for 6 months or until discharge or voluntary termination. The biostatistician will determine the cluster randomization. An ongoing process, impact and outcome monitoring plan is planned.

We will conduct an ‘enhanced usual condition’ training to identify ways that CGs communicate with family and friends to delegate challenging aspects of caregiving. Inspired by a unit of the Savvy Caregiver, the EUC will include a 30-minute presentation at sites with a follow-up 30-minute role-play regarding identifying challenging issues, ways of communication and ways to share those elements of caregiving that could be accomplished by others. When the site ‘comes on board’, the Program Manager will deliver the training and repeated every 6

months while the project is in progress for new CGs. Additionally, the staff of the EUC sites will be included in the teaching, and will facilitate discussion with the CGs during the interim. The program staff will attend the EUC site's support group every two months (or more frequently if needed) to see if CGs need guidance and discuss issues with the EUC staff.

Further, every attempt will be made to include PWDs with similar levels of cognitive/behavioral disabilities in both the PaM and EUC conditions; however, since this is cluster design, we cannot assure an equal balance.

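### Hospitalisation of persons with dementia is listed as an outcome only when judged nutrition-related, by an undefined judgement among people who know the arm; report all-cause counts by arm instead

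*Combined protocol and SAP*

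**What the plan says.** All references are to the combined protocol and SAP.

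- **Outcome list** (section D, Measures, item 4, RCC Administrator/Managers measures). Under its Outcomes heading is the discharge status of persons with dementia in the study: to institutional care, or "hospitalized related to nutrition-related problems". All-cause hospitalisation is not listed for any participant group.
- **How it is obtained** (section D, Intervention, paragraph on administrator and manager interviews). Managers are interviewed "by the Program Manager every 3 months that the study is in place" and "are asked for data regarding discharge or hospitalization of study participants to determine if the cause could be related to nutrition-related changes".
- **Research design** (section A). Managers at both PaM and EUC sites are to be interviewed about, among other things, "possible causes of discharge of PWD from the study related to nutritional problems".
- **Allocation** (section C, Study Overview). The centres are combined into two composite Sites: "These two Sites will then be randomized to PaM and EUC".
- **The interviewer's other duties.** For EUC, "the Program Manager will deliver the training and repeated every 6" months (section C, Study Overview). For PaM, the initial care plan is devised "under the direction of the Program Manager and with input from the" dietitian (section E, 1.a Sample).

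**The concern.** The data requested are unfiltered, but the listed hospitalisation outcome is filtered by cause. The filter is a judgement about whether an admission could be nutrition-related, which is a low threshold with no written definition. The plan itself recognises that causes overlap: it notes that attendees may have co-morbidities and drug treatment that affect nutritional status (section D, Intervention), and its example of an adverse event is weight loss from cardiac disease (Data and Safety Monitoring Plan, section C.4).

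PaM is a mealtime and nutrition programme. Someone who knows a participant is in PaM might be slower to call an admission nutritional, believing the programme works, or quicker, because nutrition is what that arm discusses every month. Either tendency could separate the arms on this item when admissions themselves do not differ. At stake is a descriptive statement about hospitalisation and discharge.

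**Working it through.** The plan gives no hospitalisation rate, labelling rate or between-arm analysis for this item, so there is no figure to reproduce. The check sets the sections side by side, then uses algebra without assumed numbers.

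**Step 1. Do those involved know the arm?** The documents never use the word masking, so this is inferred. Whole composite Sites are allocated, so a manager's centre is entirely PaM or entirely EUC. The Program Manager conducts the interviews, delivers the EUC training and directs the PaM plans. Both parties to the interview therefore know the allocation.

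**Step 2. Is the judgement constrained?** The interview paragraph, the outcome list and the Research design paragraph give no criteria, source documents or adjudication. The Safety Monitoring Committee determines whether an adverse event is related to study participation (Data and Safety Monitoring Plan, section C.2), which is a different question from whether an admission was nutritional.

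**Step 3. What does the filter do to a comparison?** For arm a, let

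- H(a) = hospitalisations that occur,
- c(a) = the fraction that come to the study's notice,
- q(a) = the fraction of those labelled nutrition-related.

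The listed count is L(a) = H(a) × c(a) × q(a). For arms of equal size and follow-up,

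L(PaM)/L(EUC) = [H(PaM)/H(EUC)] × [c(PaM)/c(EUC)] × [q(PaM)/q(EUC)].

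If true events and capture are equal, the first two ratios are 1 and the result is q(PaM)/q(EUC), which is labelling alone. Nothing in the plan makes the two q values equal. Since neither H nor q is given, the ratio cannot be sized and could fall on either side of 1.

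**Step 4. What does an all-cause count do?** It sets q(a) = 1 in both arms, so the third ratio drops out. The capture ratio remains, and the event ratio is still confounded with Site because there is one composite Site per arm.

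**Step 5. Is the all-cause information obtainable?**

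| Source | Section | Nutrition filter? |
|---|---|---|
| Manager interviews: discharge and hospitalisation data requested | D, Intervention | Applied only after the data are requested |
| Withdrawal reasons: death, institutionalisation, discharge from the centre | E, 1.a Sample | None |
| Adverse events and medical changes elicited at each visit and contact | Data and Safety Monitoring Plan, B.1 | None |
| Electronic record of all reported adverse events | Data and Safety Monitoring Plan, C.1 | None |
| Inpatient hospitalisation meets the definition of serious | Data and Safety Monitoring Plan, C.2 | None |

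The counts can be derived from collection already planned. What is missing is a statement that they will be reported by arm.

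**The case against.** The strongest reply is that the plan specifies no such comparison. Hospitalisation is in none of the Specific Aims. The manager-level part of Aim 2 names only satisfaction and willingness to keep the programme. The interview paragraph describes the managers' information as feasibility and evaluation data, and the Research design paragraph puts causes of discharge beside implementation barriers. The bullet itself is loose: it may be a disposition field, and the nutrition qualifier need not apply to institutional care. Unfiltered discharge and adverse event information is collected anyway.

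Most of this stands, and it keeps the point minor. It does not remove it, because the item is under an Outcomes heading, hospitalisation appears there only in its filtered form, and no unfiltered count by arm is promised.

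A reader might infer more than the documents support:

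- **That staff will decide in PaM's favour.** The interview paragraph names no decider, and the direction of any tendency is unknown.
- **That the distortion has a known size.** Any illustrative ratio would follow from the assumed labelling fractions, and an equal all-cause count would be an input to it, not a result.
- **That these counts will be used to explain withdrawals.** The plan says managers will be asked about possible causes of discharge. It describes no such use of counts.
- **That all-cause counting is free of bias.** Adverse events are elicited at each contact, and PaM adds partnership meetings and observations, so capture may be more intensive there.
- **That the committee chair could readily adjudicate without knowing the arm.** The chair reviews de-identified data for safety, but de-identified does not mean masked to arm, and judging nutritional cause would be a new task.

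**Conclusion.** The point holds as a minor one. Hospitalisation enters the outcome list only through an undefined causal judgement, reached in interviews between two people who know the arm. Any arm difference in that count could reflect attribution. The direction is unknown and no size can be given, because the documents contain no event or labelling rate.

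The conclusion rests on two readings: that knowledge of the arm follows from Site-level allocation and the Program Manager's duties in both arms, and that the nutrition qualifier applies at least to hospitalisation. It does not depend on who makes the final call.

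A reader might take this as a threat to the trial's main result. It is not one: the study is powered on weight change and change in dysfunctional behaviour, and neither passes through this judgement. Nor does the plan state a between-arm test of hospitalisation.

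**What to change.** In section D, amend the interview paragraph and the manager outcome list as follows:

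1. Report all-cause hospitalisation and all-cause discharge or institutionalisation of persons with dementia by arm, descriptively, with event dates.
2. Take the events from the manager interviews and cross-check them against the adverse event record and the withdrawal reasons. Use the full record and not only reportable events, since reportability (Data and Safety Monitoring Plan, section C.4) generally requires an event to be unexpected and at least possibly related to the study.
3. Keep the nutrition-related label as a secondary descriptor, stated to be an unmasked judgement.
4. State beside the counts that there is one composite Site per arm, that ascertainment is unmasked, and that contacts are more frequent in PaM.

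The cost is small: revised wording, recording of event dates (which the interview paragraph does not now request) and a reconciliation of sources. The price is lower specificity, because all-cause counts include admissions unconnected with meals. The change removes the attribution step only. Possible unequal capture and the confounding of arm with Site remain.
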